## 2. List of abbreviations

Abbreviation	Description
ADR	Adverse Drug Reaction
AE	Adverse event
AEMPS	Agencia Española del Medicamento y Productos Sanitarios
AR	Adverse Reaction
CD	Crohn's Disease
CDAI	Crohn's Disease Activity Index
eCRF	Electronic Case Report Form
EQ-5D	EuroQoL Questionnaire
HBI	Harvey-Bradshaw Index
HRQoL	Health Related Quality of Life
IBD	Inflammatory Bowel Disease
PMS	Partial Mayo Score
SAP	Statistical Analysis Plan
SAE	Serious Adverse Event
SIBDQ	Short Inflammatory Bowel Disease Questionnaire
UC	Ulcerative Colitis
UCDAI	Ulcerative Colitis Disease Activity Index

### **3. Study Summary**

#### **3.1. Sponsor**

Takeda Farmacéutica España S.A.

#### **3.2. Title**

Impact of co-morbidities on treatment response in inflammatory bowel disease: VERNE study

#### **3.3. Study code**

Vedolizumab-5016 (MACS-2015-101162)

#### **3.5. Participating centers and investigators**

It is estimated that 25 gastroenterology sites will participate in the study in order to ensure representativeness of all the Spanish territory.

#### **3.6. Research ethics committee**

The study protocol and other relevant documents will be submitted to Hospital Universitario y Politécnico La Fe de Valencia ethic committee.

#### **3.7. Study objectives**

The main objective of the present study is to evaluate the impact of the co-morbidities profile on treatment response in Inflammatory Bowel Disease (IBD) patients. The study also aims to describe the percentage of IBD patients exhibiting co-morbidities as well as the level of IBD severity according to the co-morbidities profile.

### **3.8. Study design**

A retrospective, non-interventional, multicentre, observational study that will include consecutive patients diagnosed with Ulcerative Colitis (UC) or Crohn's Disease (CD) who started treatment with biologics between June 2011 and June 2013.

### **3.9. Study disease**

Patients with IBD: UC and CD.

### **3.10. Study population**

Consecutive UC and CD patients that started treatment with biologics between June 2011 and June 2013 that attend a regular visit to the gastroenterology site will participate in the study. A minimum estimated sample of 200 UC patients and 200 CD patients is required. In order to avoid a biased sample (specially selection bias), patients will be recruited consecutively.

### **3.11. Study calendar**

In order to achieve the desired estimated sample, the work filed corresponding to the patients inclusion is estimated at four months. Also, time required for conducting data management, statistical analysis and preparation of the final report is estimated at three months after the inclusion of the last patient.

### **3.12. Coordination and monitoring**

The study will be coordinated by Apices Soluciones SL.

### **3.13. Study sponsor**

This study is funded by Takeda Farmacéutica España S.A.

## 4. Rationale and background

Inflammatory Bowel Disease (IBD) is a group of inflammatory disorders of the gastrointestinal tract whose etiology is believed to be a combination of genetic predisposition to gastrointestinal immune system dysregulation and environmental factors. Crohn's Disease (CD) and Ulcerative Colitis (UC) are IBD major forms and have been empirically defined by clinical, pathological, endoscopic and radiological features, exhibiting a very heterogeneous clinical profile; particularly, CD has different clinical courses and a broad spectrum of patterns, thus making it difficult to choose the best treatment. The course of IBD is characterized by two phases: relapse and remission.

UC is a relapsing non-transmural inflammatory disease that is restricted to the colon and, depending on anatomic extent, can be classified as proctitis, left-sided colitis, or pancolitis. In gastroenterology clinical practice it is usually defined as mild, moderate or severe, depending on the frequency of bloody stools. Many tools have been developed to assess UC severity. Mayo score and Ulcerative Colitis Disease Activity Index (UCDAI or Sutherland Index) were developed in the early 1980s as simplified indexes to classify UC severity and considers three clinical variables and an endoscopy score.

On the other hand, CD is a relapsing, transmural inflammatory condition that can affect the entire gastrointestinal tract, and is usually presented as discontinuous involvement of the different sections of the gastrointestinal tract which can lead to several complications (i.e. strictures, abscesses and fistulas). CD phenotype can be classified according to the Vienna criterion which is based on anatomical location and behavior of the disease. Also, the Crohn's Disease Activity Index (CDAI) was developed to quantify the symptoms of patients with CD and has been broadly used in order to define response or disease remission when assessing therapeutic options. Index values of 150 and below are associated with quiescent disease; values above that indicate active disease, and values above 450 are reported for extremely severe disease.

In terms of diagnosis, UC can be confirmed through endoscopic and histological studies, whereas CD has no definitive diagnostic, and it is usually conducted based on history, physical examination and findings from endoscopic, radiological, laboratory and histological studies.

In terms of epidemiology, some of the CD and UC highest-incidence areas of the world are northern European countries, the United Kingdom and North America. Although the incidence and prevalence of UC and CD are beginning to stabilize in these high-incidence areas, they continue to rise in low-incidence regions (i.e: southern Europe and Asia). It is estimated that 1.4 million and 2.2 million people in the United States and Europe, respectively, suffer from IBD. Spanish incidence of IBD seems to have increased in the last years, and is also variable across regions; UC incidence is estimated at 0.6-8 patients per 100,000 inhabitants per year, whereas there seems to be 0.4-5.5 CD patients per 100,000

inhabitants per year. Spanish IBD prevalence, albeit very difficult to establish, is estimated at 87-110 cases per 100,000 inhabitants per year.

The onset of IBD typically occurs in the late adolescence and beginning of adult stages of life and patients tend to progress to relapsing and chronic disease conditions. IBD is known to exert a negative impact in patient's life both in terms of Health Related Quality of Life (HRQoL) and productivity, overall representing a major burden for society and health services.

In the recent years, the aim of IBD treatment has evolved from symptomatic control to deep remission, which is defined as the absence of symptoms, markers of inflammatory activity, and endoscopic lesions, and is associated with fewer admissions to hospital, surgeries and better HRQoL. Main current treatment modalities for UC and CD include 5-aminosalicylates, corticosteroids, immunomodulators (including thiopurines, methotrexate, tacrolimus, cyclosporine, and biological therapies), and surgery. Conventional treatment with corticosteroids and immunomodulators has not been able to reduce the complications of the disease or modify its course. Over the last decade, biologic treatments, such as infliximab, adalimumab, certolizumab pegol, golimumab and vedolizumab has been used in patients with moderate to severe CD, and in those with acute severe UC who failed to respond to corticosteroids.

At present, early introduction of immunomodulators and biologic agents in patients with more serious disease is probably the most widely accepted management strategy. Treatment of IBD with anti-TNF $\alpha$  since IBD diagnosis, albeit capable of inducing and maintaining mucosal healing and reducing surgery and hospitalization rates, may imply overtreatment of patients with milder forms of disease, thus emphasizing the need for accurate prognostic markers to guide patient selection. It is worth mentioning that although anti-TNF $\alpha$  therapy is thought to be an effective approach for IBD, up to 30% of patients do not respond to induction therapy (primary non-response) and a significant proportion loses response over time (secondary non-response). Very often patients profile in randomized controlled trials is quite restrictive and not representative of patients routinely treated under usual clinical conditions, especially, in terms of presence co-morbidities, concomitant treatments and previous use of biologics.

Previous studies and reviews have been conducted in order to determine the impact of co-morbidities on treatment response in diseases like chronic obstructive pulmonary disease. However, to the best of our knowledge, this type of correlation has not been subject of study in IBD patients. Varkas *et al.* evaluated the impact of spondyloarthritis on IBD patients, but the co-morbidities profile was not analyzed. Also, Ha *et al.* conducted a study aiming to evaluate IBD management within aging population and identified previous co-morbidities as a variable related to disease progression but, again, the impact of co-morbidities profile on treatment response was not assessed.

In this context, the present study aims to study the effect of certain co-morbidities profile on treatment response by developing a co-morbidity scale to predict response to biological treatment in UC and CD patients.

## 5. Study objectives

### 5.1. Primary objective

- Evaluate the impact of the co-morbidities profile in IBD patients on treatment response to biological therapy.

### 5.2. Secondary objectives

- Evaluate the impact of Extraintestinal Manifestations profile in IBD patients on treatment response to biological therapy.
- Describe the percentage of IBD patients exhibiting co-morbidities.
- Determine the co-morbidities profile according to the level of IBD severity.

[figure not shown]
## 6. Methodology

### 6.1. Study design

In order to meet the objectives of the present study, a retrospective, non-interventional, multicentre observational study including 25 gastroenterology sites from all around Spain has been designed. Participating investigators will be gastroenterologists and will include consecutive patients diagnosed with UC or CD that started treatment with biologics between June 2011 and June 2013, after giving written informed consent. The study will consist of one only visit in which investigators will collect patients' sociodemographic (age, gender, race, level of education, smoking habits alcohol intake) and clinical (concomitant diseases, date of diagnosis, previous treatment, current treatment, disease activity when starting treatment with biologics and at the study visit, current situation in terms of treatment with biologics) data from medical charts or directly from patients (in case of discrepancy, the information coming from medical charts will be preferable). Time since patients started biological treatment until study visit or until lack of treatment response or until treatment change will constitute the reference period for the study. In order to fulfill current legislations regarding non-interventional studies, investigators will commit to follow usual clinical practice.

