#### **6.3.2. Inclusion criteria**

- Adult patients (aged  $\geq 18$ )
- Patients diagnosed with UC or CD according to the "World Gastroenterology Organization Practice Guidelines for the Diagnosis and Management of IBD in 2010"
- Patients naive to biologics that started treatment with biologics between June 2011 and June 2013
- Patients in whose biological treatment was prescribed according to daily clinical practice.
- Patients that gave written informed consent

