#### 6.4.3. Data collection

25 gastroenterology centers (one investigator per center) from all around Spain will participate in the study. In order to achieve the minimum sample, each gastroenterology specialist will have 4 months to include approximately 8 UC and 8 CD consecutive patients that fulfill the inclusion/exclusion criteria specified on sections 6.3.2 and 6.3.3. Investigators will inform patients about the study objectives and

methodology and patients will have to give written informed consent before inclusion in the study as specified on section 6.3.5.

Investigators will collect sociodemographic and clinical data from patients' records specified on section 6.4.3 and will introduce it in the eCRF.

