- Urogenital manifestations of IBDComorbidities in UC and CD patients (defined as the coexistence of another medical condition alongside IBD, and does not imply causation) at the time of diagnosis and at the study visit, will be listed according to chosen according to the Charlson index:

Comorbidity Component	Score
Myocardial Infarction	1
Congestive Heart Failure	1
Peripheral Vascular Disease	1
Cerebrovascular Disease	1
Dementia	1
Chronic Obstructive Pulmonary Disease	1
Connective Tissue Disease	1
Peptic Ulcer Disease	1
Diabetes Mellitus	1 (mild), 2 (moderate- severe)
Moderate-Severe      Chronic      Kidney Disease	2
Hemiplegic	2
Leukemia	2
Malignant Lymphoma	2
Solid Tumor	2 (tumor), 6 (if metastasis)
Liver Disease	1 (mild), 3 (moderate-severe)
Acquired immunodeficiency syndrome (AIDS)	6

- Biological treatment/s for UC or CD followed during the reference period:
  - Starting date
  - Posology
  - Intensification of biological treatment: date and type of intensification
  - Continuing with the treatment
  - Date and reason for discontinuation, if applicable
  - New biological treatment prescribed after discontinuation, starting date, posology, continuing with the treatment, date and reason for discontinuation.
- Concomitant treatment with corticosteroids (e.g. prednisone, hydrocortisone, betamethasone, methylprednisolone, etc,) or immunosuppressives (e.g. Ciclosporin, Methotrexate, etc) during induction phase
  - Starting date, number of cycles

Other treatments followed before the reference period to be chosen from the following list:

- Aminosalicylates (e.g. mesalazine, Sulfasalazine, 5-ASA, etc), oral, enema, suppository.
- Corticosteroids (e.g. prednisone, hydrocortisone, betamethasone, methylprednisolone, etc), oral, enema, suppository.
- Thiopurines (e.g. azathioprine, mercaptopurine, etc).
- Immunosuppressives (e.g. Ciclosporin, Methotrexate, etc).
- Anti-diarrheal drugs.
- Pain medications.
- Antidepressants.
- Antibiotics.
- Use of alternative medicine (e.g. acupuncture, relaxation therapy, Qigong, herbal therapy, etc).
- Other (specify)

- Other treatments followed during the reference period to be chosen from the following list:
  - Aminosalicylates (e.g. mesalazine, Sulfasalazine, 5-ASA, etc), oral, enema, suppository.
  - Corticosteroids (e.g. prednisone, hydrocortisone, betamethasone, methylprednisolone, etc), oral, enema, suppository. Number of cycles
  - Thiopurines (e.g. azathioprine, mercaptopurine, etc).

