#### 6.4.5. Main outcome

Non responders will be those patients not achieving a reduction in HBI of at least 2 points from baseline for CD, and a decrease in the PMS of at least 2 points for UC.. In the cases where these indexes are not available, clinical response will be evaluated according to physician criteria at short term (10 weeks after starting the anti-TNF) and at long term (at least 6 months after starting the anti-TNF). Primary non-responders (PNR) were defined as patients with no clinical response at short term. Loss of response (LOR) was defined as loss of the effect of the drug along the follow up in a patient with initial response.

Reasons to stop the drug will be classified as follows: PNR, LOR, side effects (SE), remission and other.

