7. EFFICACY ASSESSMENT

7.1. Efficacy Assessment; general considerations

Non responders will be those patients not achieving a reduction in HBI of at least 2 points from baseline for CD and a decrease in the PMS of at least 2 points for UC.

In the cases where these indexes are not available, clinical response will be evaluated according to physician criteria at short term (10 weeks after starting the anti-TNF [*primary response and primary non-response*]) and at long term (at least 6 months after starting the anti-TNF [*primary response maintenance and loss of response*]).

We will calculate the following variables:

- **Lack response during the induction phase (primary non response):** Those patients who 10 weeks after starting the anti-TNF not achieving a reduction in HBI of at least 2 points from baseline for CD and a decrease in the PMS of at least 2 points for UC. In the cases where these indexes are not available, clinical response will be evaluated according to physician criteria at short term (*primary response and primary non-response*).
- **Loss of response during the maintenance phase (secondary loss of response):** Those patients who at least 6 months after starting the anti-TNF not achieving a reduction in HBI of at least 2 points from baseline for CD and a decrease in the PMS of at least 2 points for UC. In the cases where these indexes are not available, clinical response will be evaluated according to physician criteria at short term (*primary response maintenance and loss of response*).

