7.2. Primary efficacy endpoint

- **Primary endpoint:** Evaluate the impact of the co-morbidities profile in IBD patients on treatment response to biological therapy.

The analysis that will be performed to answer the objective will be the following:

In order to determine the level of correlation between the co-morbidities profile and treatment response, adjusting for sociodemographic and clinical profile of patients, two logistic regression models will be conducted. The dependent variable of the models will be the **lack of response during the induction phase and the loss of response during the maintenance phase**. In both models independent variables will include all comorbidities, as well as sociodemographic and clinical variables as covariates.

- The following potential variables will be considered for the analysis:
 - Crohn's Disease or Ulcerative Colitis.
 - Myocardial Infarction (yes/no).
 - Congestive Heart Failure (yes/no).
 - Peripheral Vascular Disease (yes/no).
 - Cerebrovascular Disease (yes/no).
 - Dementia (yes/no).
 - Chronic Obstructive Pulmonary Disease (yes/no).
 - Connective Tissue Disease (yes/no).
 - Peptic Ulcer Disease (yes/no).
 - Mild Chronic Hepatopathy (yes/no).
 - Diabetes Mellitus (yes/no).
 - Hemiplegic (yes/no).
 - Moderate-Severe Chronic Kidney Disease (yes/no).
 - Diabetes with lesions in target organs (yes/no).
 - Solid Tumor (yes/no).
 - Leukemia (yes/no).
 - Lymphoma (yes/no).

- Moderate-Severe Chronic Hepatopathy (yes/no).
 - Solid tumor with metastases (yes/no)
 - Acquired immunodeficiency syndrome (AIDS) (yes/no).
 - Gender.
 - Race (caucasian, asiatic, latin, black, other).
 - Level of education (uneducated, primary education, secondary education, university education).
 - Working status (student, self-employed, employed by other, retired, housework, unemployed, temporarily unable to work, permanently unable to work, other).
 - Smoking habits (non-smoker, ex-smoker and smoker).
 - Alcohol abuse (yes/no).
 - Time from diagnostic of disease.
 - Disease location.
 - Discontinuation the biological treatment (yes/no)
- Each one of the variables will be compared between the subjects with primary non-response vs primary response and primary response maintenance vs loss of response and those variables whose p-value is lower than 0.1 are considered potential variables for performing a logistic regression analysis.

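### Loss of response is a yes/no logistic outcome with no fixed time horizon and no stated place for patients who stop for other reasons, so the comorbidity odds ratio can be biased in a direction the plan leaves open

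*Protocol*

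**What the plan says.** SAP 7.2 states that "two logistic regression models will be conducted", one for primary non-response and one for LOR; Protocol 7.4 plans the same. The LOR model compares patients who maintained their primary response with patients who lost it.

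Three features of the plan determine how long each patient can be observed to lose response:

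- **Observation window.** Protocol 6.1 runs it from the first biologic "until study visit or until lack of treatment response or until treatment change will constitute the reference period".
- **Start and visit dates.** Protocol 6.3.2 admits "Patients naive to biologics that started treatment with biologics between June 2011 and June 2013". Under Protocol 6.4.3, "each gastroenterology specialist will have 4 months to include approximately 8 UC and 8 CD consecutive patients".
- **LOR definition.** Protocol 6.4.5: "Loss of response (LOR) was defined as loss of the effect of the drug along the follow up in a patient with initial response". SAP 7.1: "Those patients who at least 6 months after starting the anti-TNF not achieving a reduction in HBI of at least 2 points", with the matching Partial Mayo rule for ulcerative colitis and physician judgement as fallback. Six months is a minimum, not a fixed assessment time.

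Stops for other causes are kept apart from LOR. Protocol 6.4.5: "Reasons to stop the drug will be classified as follows: PNR, LOR, side effects (SE), remission and other". SAP 6.1 adds partial response (PR) to that list. Among the timing data, Protocol 6.4.4 collects the start date, the intensification date and "Date and reason for discontinuation, if applicable". It lists no date for LOR itself.

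Neither document includes a follow-up term, a censoring rule, a competing event or a time-to-event analysis. Neither says how a patient who stopped for a reason other than LOR is coded in the LOR model. SAP 7.2 does list discontinuation of the biologic (yes/no) as a candidate covariate, and Protocol 7.4 allows an optional separate analysis of patients who switched biologic.

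**The concern.** A patient who stops after a few months for side effects has had little time to lose response on the drug, whereas one still on treatment at the visit may have had years. A yes/no outcome without time treats the two alike, or leaves the first patient out, or counts that patient as a failure, depending on a coding choice that the SAP does not make.

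This matters most if stopping for other reasons is related to comorbidity. The documents do not show that it is. But comorbidity is the exposure in the primary objective, so this is the dependence the analysis has to withstand. At stake are the size and the sign of the comorbidity odds ratios in one of the two primary models.

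**Working it through.** **1. The plan's own figure.** Protocol 7.1 uses 10 events per variable, 10 variables and a 50% event rate: 10 × 10 / 0.50 = 200 per disease. This reproduces. The rule contains no time, so it neither reveals the problem nor changes with the fix.

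**2. Spread of potential follow-up.** Starts span 24 months and visits span 4, so potential follow-up differs by up to about 24 + 4 = 28 months before anyone stops early.

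**3. Effect of competing stops.** The documents give no rates, so all of these are assumptions: LOR hazard l = 0.10 per year in both groups (true hazard ratio 1.00), hazard of other stopping m = 0.05 per year without and 0.20 with comorbidity, T = 4 years.

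P(LOR by T) = l/(l+m) × (1 − exp(−(l+m)T))

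P(other stop by T) = m/(l+m) × (1 − exp(−(l+m)T))

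P(neither) = exp(−(l+m)T)

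| | No comorbidity | Comorbidity |
|---|---|---|
| (l+m)T | 0.60 | 1.20 |
| P(LOR) | 0.3008 | 0.2329 |
| P(other stop) | 0.1504 | 0.4659 |
| P(neither) | 0.5488 | 0.3012 |

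The three possible codings of the other stops give:

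| Coding | Odds, comorbidity | Odds, none | OR |
|---|---|---|---|
| No LOR | 0.2329/0.7671 = 0.304 | 0.3008/0.6992 = 0.430 | 0.71 |
| Excluded | 0.2329/0.3012 = 0.773 | 0.3008/0.5488 = 0.548 | 1.41 |
| LOR | 0.6988/0.3012 = 2.320 | 0.4512/0.5488 = 0.822 | 2.82 |

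With LOR at 0.10 to 0.25 per year, other stopping at 0.05 versus 0.10 to 0.30 per year, and 3 to 5 years of follow-up, the ranges are 0.40–0.91, 1.08–2.29 and 1.27–5.72.

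**4. If comorbidity is truly harmful.** With hazard ratio 1.5, LOR 0.15 per year without comorbidity and 5 years, the no-LOR coding gives OR 0.97 when comorbid patients stop for other reasons at 0.20 per year and 0.73 at 0.30. Under that coding real harm can vanish or reverse.

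**5. Simulation of the no-LOR coding.** Assumptions: 400 patients, 15% with the comorbidity, follow-up uniform over 3 to 5 years, LOR 0.15 per year in both groups, other stopping 0.05 per year without comorbidity, 400 runs per scenario. With comorbid stopping at 0.10, 0.20 and 0.30 per year, the median logistic OR was 0.84, 0.67 and 0.54. A falsely significant protective effect appeared in 10%, 23% and 52% of runs. Cause-specific Cox regression gave hazard ratios of 0.97 to 0.99, with such findings in 2% to 3% of runs.

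**6. Unequal follow-up alone.** Use the same formula with other stopping at 0.05 per year in both groups and LOR at 0.05 to 0.20 per year. If one group is followed for 5 years and the other for 3, the OR is 1.65–1.82, but that is a worst case. A difference of 4 versus 3.75 years gives about 1.06–1.08. If follow-up is unrelated to comorbidity, no spurious association arises from this source.

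**7. The discontinuation covariate.** Suppose every LOR leads to stopping. Among patients who stopped, in the scenario of step 3, the odds of LOR against another reason are 0.10/0.20 = 0.5 with comorbidity and 0.10/0.05 = 2 without. Their ratio is 0.25, although the true hazard ratio is 1.00. Adjusting for this variable does not remove the bias and can add to it.

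**The case against.** A reader might infer that early stoppers for side effects count as maintained responders, so that comorbidity will look protective. The documents do not support that. They assign such patients to neither group, and the other two codings push the odds ratio above 1. The SAP's own definition could even place some of them in the LOR group: Protocol 6.4.4 records the indices at the start of the reference period and at the study visit, so LOR may be a status at the visit, and an early stopper with active disease then would count as LOR. The formulas above fit the Protocol's notion of loss along follow-up better than this status reading.

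A reader might also infer that all the dates needed are already collected. They are not: a patient who loses response without stopping has no LOR date.

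There is also a fair point about the target. Protocol section 4 speaks of a scale to predict response. For prediction, the absolute risk of LOR in the presence of other stopping is a legitimate quantity, and a lower observed risk in comorbid patients would be real, though not evidence that comorbidity protects. The word bias here is relative to the LOR rate. But even a prediction target needs a stated horizon and a stated coding of other stops, and the plan gives neither.

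Finally, every rate above is assumed, and no passage shows that comorbid patients stop more often or were followed for less time. This limits what can be said about size. It does not fill the gap in the plan.

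**Conclusion.** The concern holds as a gap with undetermined direction. One of the two primary models uses a binary outcome without a horizon, over unequal observation time, and has no rule for patients who stop for side effects, remission, PR or other reasons. If such stopping differs by comorbidity, each simple coding departs from the true LOR rate ratio: 0.71, 1.41 or 2.82 against 1.00 in the central scenario. That result rests on constant hazards, a fourfold difference in other stopping and 4 years of follow-up, all assumed. If other stopping and follow-up do not depend on comorbidity, the spurious association disappears. Neither the discontinuation covariate nor the optional analysis of switchers resolves the matter. It should be settled in the SAP before the data are seen, because the coding choice can decide the sign of the result.

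**What to change.** - In initial responders, add a cause-specific Cox model for LOR from the end of induction. Censor at the study visit and at stopping for side effects, remission or other reasons. Show cumulative incidence with those stops as competing events.
- State whether a stop for PR is an event or a competing event.
- Add an LOR date to the eCRF, taken from the chart. Failing that, use the discontinuation date when the recorded reason is LOR, and say that the endpoint then becomes discontinuation for LOR.
- Remove discontinuation (yes/no) from the candidate covariates of the LOR model, because it arises after baseline and is partly a consequence of LOR.
- Keep the logistic model as supportive, state how stops for reasons other than LOR are coded, and show the alternative codings beside it.

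The cost is SAP wording, one added model with its curves, and one more charted date for patients who lost response without stopping. No extra visit is needed. The drawback is that LOR dates will be only as exact as the charts.
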